Study Cover Page

Official Study Title: Treatment of Prolonged Grief Disorder in Combat Veterans

NCT02283333

Protocol date: August 4, 2014

Data Analytic Plan

Baseline data were compared across groups using t-tests for continuous variables and chi-square tests for proportion variables to examine differences in demographic factors, pre-treatment symptom intensity (i.e., grief, depression, and PTSD), and co-variates that are particularly relevant to research with veterans (i.e., social support, time since death, and overall number of sessions completed). No differences in scores or proportionate representation were noted in terms of any demographic, baseline symptoms, or potential covariates. Next, repeated measures analysis of variance were conducted to determine the relative effectiveness of BATE-G vs. CT-G in terms of grief (i.e., ICG-R), depression (i.e., BDI-II) and PTSD (i.e., PCL-5) symptom outcomes. Although no covariation control (i.e., ANCOVA) was employed because covariates did not differ between groups. Baseline scores on primary dependent measures were included in the ANOVA model to test overall effects of time. The intent to treat (ITT) sample served as the primary analytic sample, and missing data were conservatively replaced through total sample mean substitution, which shares variance of missing data across groups and lessens likelihood of finding spuriously significant results. All analyses were repeated with the 'per protocol' sample, here defined as those who completed at least 5 of the 7 sessions specified in each treatment protocol. No differences in statistical significance were noted for any variable between ITT and per protocol samples, and thus the ITT sample data alone are reported.

Protocol

SIGNIFICANCE

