We have recently published BATE-G pilot data from our National Institutes of Health funded R21 project (**R21AG023495**) that supports the proposed treatment (Acierno et al., 2012). This treatment includes a video component as well as an accompanying brochure to reinforce the intervention content. The present proposal will involve specific adaptations of the video portion of the intervention for Veterans, followed by a randomized controlled trial (RCT) to evaluate its effectiveness in reducing PGD. Pilot study participants were 22 women and 4 men (M age = 65.6 years; SD = 10.5) referred by agencies that served bereaved individuals, university hospital nurse supervisors, or self-referred in response to posted brochures. Mean number of days since death upon study enrollment was 180 (SD = 196.1; range = 24-884), indicating the intervention is applicable both to recent and delayed loss reactions. One week following completion of an initial assessment battery by the study interviewer, participants met with a BATE-G study therapist in person for about 75 minutes for the initial session. To demonstrate the exportability of this treatment to counselors of various degrees of training, therapists ranged from BA level community agency counselors to PhD intern candidates. At pre-treatment, 34.6% met full criteria for complicated bereavement / PGD (not considering the 6 month post-death requirement). By post-treatment, only 7.7% met criteria. Figures 1-4 (below) provide graphical illustration of the most relevant outcome data in the form

of pre-post treatment overlaid scatter plots for each continuous dependent measure, illustrated in terms of the number of days post-death, which served as the covariate in all analyses. Note that each participant's pre- and post-treatment scores are joined by a vertical line illustrating change after treatment; note also that virtually every participant improved.

Figure 1: Scatter plot of Complicated Grief Assessment Int. scores

[figure not shown]

Figure 2 Scatter Plot of Pre-post PTSD symptom count

[figure not shown]

Figure 3: Scatter plot of pre-post MDD symptom count scores

[figure not shown]
[figure not shown]

Figure 4: Scatter plot of SF-36 Social Functioning (higher is better)

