We will use a 2 x 4 (treatment by time) randomized controlled trial design to compare the BATE-G treatment for PGD to the VA/DoD recommended treatment for PGD: Cognitive Restructuring and Supportive Grief Counseling (from the *Iraqi War Clinician Guide, 2nd ed.*) *currently the best practices treatment advocated by VA/DoD for Veterans at Veterans Affairs Medical Center (VAMC) facilities with bereavement.* Dependent measures will include assessment of both psychological and health-related functioning at pre- treatment, post-treatment (approx 8 weeks later), and at 3 & 6 months post treatment follow up to demonstrate effectiveness of the treatment. Participants will be 140 active duty Veterans of OIF/OEF/OND or discharged Veterans of OEF/OIF/OND service who meet PGD cutoff criteria, but not criteria for PTSD, and who present for services at the VA Medical Center, Charleston. The componential BATE-G treatment (15-minute video and therapy), offered in a combined in person / televideo package, will be compared to individual Cognitive Restructuring and Supportive Grief Counseling delivered in the same number of sessions & format (a combination of in person and televideo). Participants who complete treatment and follow-up assessments will be 140 OEF/OIF/OND Veterans who meet PGD cutoff criteria outlined below. Assignment to treatment condition will be evenly distributed and randomly determined using a method identical to that of our two ongoing treatment outcome studies for PTSD in Veterans and described below.

Participants and Inclusion/Exclusion Criteria. Participants will be 140 Active Duty Service Personnel / Veterans of OIF, OEF, or OND: Participants will be male or female, age 21 and above, with PGD. Actively psychotic or demented persons, individuals with both suicidal ideation **and** clear intent, or individuals with significant homicidal ideation and or intent, and individuals meeting criteria for substance dependence will be excluded from participation; however, in order to maximize generalization of results, presence of other forms of psychopathology will not be a basis for exclusion. All structured interviews will be audiotaped to calculate inter-rater reliability on a randomly selected 20%. A 4-week medication stabilization will be required.

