Treatment Integrity and Training. Counselors will receive the video and brief treatment manual and will be asked to review these prior to a 4-hour training with the study PI. At this training, the study PI will go over key points of the intervention outlined above. A key treatment tool, the video, has been specifically designed as a treatment training mechanism in itself. In addition, all treatment sessions will be audio taped and 20% of case tapes will be reviewed for treatment integrity by two trained independent raters according to session checklists. In this way, we will assure that directive treatment procedures found in the BATE-G condition are not delivered in Cognitive Restructuring and Supportive Grief Counseling.

Treatment Providers. Treatment providers will be master's level counselors with at least 2 years of experience providing bereavement counseling to adults. All providers will perform both treatments.

HIPAA Compliance for Home-Based Televideo Equipment. In order to assure patient Confidentiality and HIPAA compliance, we will use the MUSC/Charleston VAMC contracted version of HIPAA compliant software for televideo patient care. If participants do not have a computer, we will supply them with a tablet for use during the study, as we have done with our two ongoing telemedicine treatment studies with Veterans.

Dependent Measures & Interviewers. All measures will be administered by master's level research assistants who are blind to experimental condition and who achieve interrater reliability on 5 practice assessments of 90%. All participants in both conditions will complete most measures at pre-treatment/baseline (at least 6 months post-death), post-treatment, and 3 & 6 months post-treatment. The timing of assessments with study procedures is described in the diagram below. In pilot testing of the assessment battery, 42 minutes was the average time of completion for self report, with another 30-40 minutes necessary for the selected modules of the Structured Clinical Interview for DSM 5.

DOMAIN	MEASURE	DESCRIPTION	TIMING
Demographics	Race Gender etc.	Descriptive self-report	Baseline
Prolonged Grief Disorder	Inventory of Complicated Grief, Revised (Prigerson, et al, 2001)	34item self-report; total intensity score; high reliability, concurrent validity with BDI & satisfactory criterion validity (Prigerson et al., 1995; 1997; Silverman et al., 2000; 2001)	Base, Post-Tx, 3 & 6 month

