Selected Axis I Mental Diagnoses	Structured Clinical Interview for DSM-5 (To Be released)	Clinician administered, gold standard; Dx: Major Depression, Panic Disorder, Generalized Anxiety Disorder, PTSD, Sub. Use Disorder. (Last version TBA)	Base, Post-Tx, 3 & 6 month

Depression	Beck Dep Inventory-II (Beck et al, 1996)	21 item self-report; high reliability and concurrent validity (Beck, Steer, & Brown, 1996)	Base, Post-Tx, 3 & 6 month
PTSD	PTSD Symptom Scale (Foa et al., 1993)	17 item self-report; 3 subscales. High reliability and concurrent validity (Foa et al., 1993)	Baseline, Post-Tx 3 & 6 month

Power Analysis. The primary longitudinal efficacy outcome variables are: intensity of PGD symptoms (ICG), and depression symptom severity (BDI) and PTSD (PCL) variables. In several studies of behavioral activation for mood disorders by Lejuez and colleagues (Hopko, Lejuez, & Hopko, 2004; Hopko et al., 2003; Lejuez et al., 2011, Lejuez, Hopko, & Hopko, 2001; MacPherson et al., 2010), effect sizes of .7 to 1.5 were obtained. In addition to behavioral activation, the present intervention also includes a video-based treatment for PTSD-like symptoms of complicated bereavement based on our existing treatment for PTSD in combat Veterans. In the pilot study, this treatment achieved an effect size of 0.7 on psychological outcomes, and .25-.3 on health outcomes. For comparing the longitudinal profile of continuous outcomes for the BATE-G versus Comparator groups across the study period [assuming 4 measurement time points, level of significance alpha=0.05, two-tailed comparison, correlation between pairs of measurements within subjects (interclass correlation) no larger than p=0.5], we estimate that with 44 subjects per group (88 total), we will have approximately 90% power to detect a standardized effect size of at least 0.35 (difference in comparison group means in units of standard deviation (sd)). For outcome variables having standard deviations (sd) in the range 5-15, for example, the raw effect sizes that can be detected range from approximately 2.3 to 6.9 raw units. To account for attrition during treatment (28%), and loss to followup (10-15%), we inflate the sample size accordingly to achieve a final sample size of approximately 140 subjects: 140 x 28% attrition = 101; 101 x 12% loss = 89 total participants completing all measures (note, ITT sample size will be 28% larger than power estimate requires, as treatment dropouts are included in ITT analyses).

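### Three scales are called primary with one undivided 0.05 and no success rule; if any one counts, the chance of a false between-group difference is about 10% to 14%, and about 5% to 7% in favour of BATE-G

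*Combined protocol and SAP*

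**What the plan says.** Power Analysis: "The primary longitudinal efficacy outcome variables are: intensity of PGD symptoms (ICG), and depression symptom severity (BDI) and PTSD (PCL) variables". The three scales share the primary label without ranking. The bracketed assumptions of the same paragraph give "level of significance alpha=0.05, two-tailed comparison". This is the only alpha in the documents, and it is not divided among the scales.

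Data Analytic Plan: repeated measures ANOVA compares the two treatments on "grief (i.e., ICG-R), depression (i.e., BDI-II) and PTSD (i.e., PCL-5) symptom outcomes". The section again refers to primary measures in the plural. It states no alpha, testing order, adjustment or success rule. Its one remark about avoiding spurious significance concerns mean substitution for missing values. The section reports finished work: "No differences in statistical significance were noted for any variable between ITT and per protocol samples".

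Research Design and Methods describes a "2 x 4 (treatment by time) randomized controlled trial design". Either the group effect or the group-by-time interaction could therefore carry the comparison, and the documents do not say which one does.

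Preliminary Studies describes the present proposal as adapting the video, "followed by a randomized controlled trial (RCT) to evaluate its effectiveness in reducing PGD". The measures table under Dependent Measures & Interviewers assigns the ICG-R to prolonged grief disorder and credits it with "concurrent validity with BDI".

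**The concern.** Three outcomes share the primary label and nothing says how their results combine into a conclusion. The grief result is easy to identify. What is missing is whether a difference on the depression or PTSD scale alone would count as a positive trial.

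If it would, two things follow. The 0.05 no longer describes the chance of a false primary claim. And the trial could be reported as a primary success with no effect on grief, although reducing prolonged grief is its purpose. The Significance section argues that prolonged grief differs from depression and PTSD in symptoms and in response to treatment, so success on those scales cannot stand in for success on grief.

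**Working it through.** **Inputs.** Three primary scales (Power Analysis, Data Analytic Plan). Two-sided 0.05 per scale (Power Analysis; assumed to be the level used in the analysis). The between-scale correlation r is not in the documents; it is assumed equal for all pairs and varied from 0 to 0.8. The within-subject correlation of 0.5 in the Power Analysis links visits, not scales, and does not supply it. The documents give no error rate for the three scales together, so there is no plan figure to reproduce first.

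**Independent scales.**
- Either direction: 1 − 0.95³ = 1 − 0.8574 = 0.1426.
- Favouring BATE-G on at least one scale: 1 − 0.975³ = 1 − 0.9269 = 0.0731.
- One scale alone: 0.05 and 0.025.

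**Correlated scales.** With c = 1.960 and X standard normal, for a one-degree-of-freedom contrast on each scale:
- Either direction: 1 − E{[Φ((c − √r·X)/√(1−r)) − Φ((−c − √r·X)/√(1−r))]³}
- Favouring BATE-G: 1 − E{[Φ((c − √r·X)/√(1−r))]³}

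Numerical integration gives:

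| r between scales | any false difference | false difference favouring BATE-G |
|---|---|---|
| 0 | 14.3% | 7.3% |
| 0.5 | 12.5% | 6.3% |
| 0.8 | 9.8% | 4.9% |

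**Does the choice of test matter?** For the three-degree-of-freedom group-by-time test, simulation gives 12.8% at r = 0.5 and 10.1% at r = 0.8, so the either-direction figures barely change. That test has no single direction, so the right-hand column applies only to a one-degree-of-freedom contrast.

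**If all three scales had to be significant.** With no true effect on any scale, the chance is 0.05³ = 0.01% at r = 0, 0.3% at 0.5 and 1.4% at 0.8. Whichever scales truly lack an effect, it cannot exceed 5%.

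**Effect of Holm adjustment.** With no true effects, the chance of any false difference equals that of testing each scale at 0.05/3 = 0.0167: 4.92% at r = 0, 4.45% at 0.5 and 3.53% at 0.8.

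**Power under Holm.** Take the plan's 90% per scale as given. The standardized effect is then 1.960 + 1.282 = 3.242. The critical value at 0.0167 is 2.394, so power at the first step is Φ(3.242 − 2.394) = Φ(0.848) = 0.80. Later steps are less strict. If all three effects are real, simulation with 2,000,000 draws gives average per-scale power of 88% (r = 0), 87% (0.5) and 85% (0.8). Power for at least one scale is 99%, 95% and 90%.

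**The case against.** The strongest reply is that the any-one-scale premise is not in the documents. Grief is listed first, the ICG-R is its assigned measure, and the purpose is to reduce prolonged grief. Read scale by scale, each claim carries its own 5%; read as requiring all three, nothing is inflated. The 0.05 is also only a power input. All of this stands, and it makes the inflation conditional. It does not supply the missing rule: the depression and PTSD scales carry the same primary label, and no text says what a difference on one of them alone would mean.

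A reader might infer that the trial's chance of falsely declaring BATE-G superior is 10% to 14%. The figures do not support that. The range counts differences in either direction; the part favouring BATE-G is about half. A reader might also infer that the plan adopted an any-one rule, or that the grief result cannot be singled out. The documents show neither.

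Correlation between the scales is a fair objection to 14.3%. The measures table reports concurrent validity of the ICG-R with the BDI, so independence is an upper bound rather than the expected case. The lower end depends on stopping at 0.8; at 0.9 the either-direction figure is 8.4%, still above 5%.

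The remark about conservative mean substitution does not answer the point. It concerns missing data and sets no error rate across three outcomes.

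**Conclusion.** The concern holds as a gap in the interpretation rule, not as a demonstrated false-positive rate. With three primary scales and no order, adjustment or success criterion, an any-one-scale claim would carry roughly two to three times the nominal error: 9.8% to 14.3% against 5% in either direction, or 4.9% to 7.3% against 2.5% in favour of BATE-G.

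This rests on three assumptions: each scale is tested once at two-sided 0.05, any one significant scale is presented as success, and between-scale correlations lie between 0 and 0.8. Whether adjustment would change any conclusion depends on results that these documents do not show. The point merits correction in the report and does not invalidate the trial.

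**What to change.** Because the analyses are reported as complete, correct the reporting:

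1. Name the one between-group test used for each scale, for example the group-by-time interaction.
2. Report all three scales with Holm-adjusted p-values beside the unadjusted ones. This holds the family-wise error at or below 5%.
3. State that a difference on the depression or PTSD scale alone does not establish the aim of reducing prolonged grief.
4. Label any ordering of the scales as post hoc.

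Cost: no new data, three adjusted p-values and a few sentences. The loss of power is modest. If each scale truly had 90% power and all three effects were real, average per-scale power under Holm would stay at about 85% to 88%. It would be about 80% for a scale that must pass at the first step, 0.0167.

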ANCOVAs revealed that neither the covariate (days since death) nor its interaction with the independent variable was significant. Therefore, focus was turned to the main effect of time (pre-post treatment change). **Complicated Grief (CGA-I)** scores were reduced from a mean of 23.4 (SE = 1.3) to a mean of 18.2 (SE = 1.2) $p < .001$, effect size partial $\eta^2 = .46$; **PTSD** symptom count scores were reduced from 8.0 (SE = 0.6) to 4.3 (SE = 0.7) $p < .001$, $\eta^2 = .41$; **MDD** symptom count scores were reduced from 5.2 (SE = 0.4) to 2.8 (SE = 0.5), $p < .01$, $\eta^2 = .38$. **BDI** scores were reduced from 19.9 (SE = 2.4) to 12.7 (SE = 2.0) $p < .01$, $\eta^2 = .27$; the **SF-36 Social Functioning** scale was significantly improved from 52.7 (SE = 5.6) to 64.7 (SE = 5.4) $p \leq .05$, $\eta^2 = .17$.

These data support the feasibility and initial efficacy of BATE-G, a highly portable intervention for PGD designed around the principles of behavioral activation and therapeutic exposure, as well as logistic aspects of the treatment such as patient safety protections for home based treatment and patient use of technology.

RESEARCH DESIGN AND METHODS

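### The stated 90% power for 0.35 SD with 44 per group does not follow from the plan's own inputs (about 54% for a time-averaged comparison at correlation 0.5), and the raw-unit range and completer counts contradict the same paragraph

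*Combined protocol and SAP*

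**What the plan says.** The Power Analysis paragraph of the protocol sets out four time points, two-sided alpha 0.05 and a "correlation between pairs of measurements within subjects (interclass correlation) no larger than p=0.5". From these it concludes that "with 44 subjects per group (88 total), we will have approximately 90% power to detect a standardized effect size of at least 0.35". A parenthesis defines that effect size as the "difference in comparison group means in units of standard deviation (sd"). The paragraph speaks of comparing longitudinal profiles but names no test.

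The next sentence takes outcome SDs of 5 to 15 and says that "the raw effect sizes that can be detected range from approximately 2.3 to 6.9 raw units". The paragraph then applies 28% attrition and 12% loss to follow-up to 140 participants and arrives at "89 total participants completing all measures (note, ITT sample size will be 28% larger than power estimate requires").

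In support of the effect size it states: "In the pilot study, this treatment achieved an effect size of 0.7 on psychological outcomes". Research Design and Methods says: "Participants who complete treatment and follow-up assessments will be 140 OEF/OIF/OND Veterans". The Data Analytic Plan describes repeated measures ANOVA with baseline as one of the time points, and says that no ANCOVA was used.

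**The concern.** A power statement can be checked when it gives the sample size, the number of visits, the correlation, alpha and an effect in SD units. This one gives all five, and 90% does not come out at the stated correlation bound. The paragraph also offers two detectable effects, 0.35 SD and, through the raw units, 0.46 SD.

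The paragraph is the trial's only sample-size justification, and the comparator is an active treatment matched in number of sessions and delivery, so modest differences matter. A non-significant result would be read as good evidence against a 0.35 SD difference. With time-averaged power of 54%, a true difference of that size would be missed about 46% of the time.

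The pilot effect of 0.7 does not settle the matter. Preliminary Studies describes one treated group of 26, in which "focus was turned to the main effect of time (pre-post treatment change"). That is change over time in a single group, not a difference between two treatments.

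**Working it through.** **Inputs (Power Analysis).** n = 44 per group; m = 4 time points; alpha 0.05 two-sided; correlation ρ up to 0.5; d = 0.35 SD. I assume equal correlation between visits and complete data for the n shown.

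**Step 1: the plan's 90%.** For a comparison of the two groups' means over the four visits, the variance factor is v = (1 + 3ρ)/4. The noncentrality is d / √(2v/n), with 2n − 2 = 86 degrees of freedom.

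- ρ = 0: v = 0.25; 0.35 / √(0.5/44) = 3.283; power 90.1%.
- ρ = 0.5: v = 0.625; 0.35 / √(1.25/44) = 2.077; power 53.7%.

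| ρ | Power for 0.35 SD | Power for 0.46 SD |
|---|---|---|
| 0 | 90% | 99% |
| 0.1 | 81% | 96% |
| 0.2 | 73% | 92% |
| 0.3 | 65% | 87% |
| 0.4 | 59% | 82% |
| 0.5 | 54% | 77% |

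The largest ρ that still gives 90% is 0.001 for 0.35 SD and 0.244 for 0.46 SD. Power falls as ρ rises, so for this test the bound of 0.5 is the worst case, where the claim ought to hold.

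**Step 2: other sample sizes at ρ = 0.5.**

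| n per group | Power for 0.35 SD | Difference detectable with 90% power |
|---|---|---|
| 44 | 54% | 0.55 SD |
| about 62 (treatment dropouts kept) | 68% | 0.46 SD |
| 70 (all randomised) | 74% | 0.44 SD |

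At 44 per group, 0.553 SD is 0.553 × 5 = 2.8 to 0.553 × 15 = 8.3 raw units.

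**Step 3: other tests, 0.35 SD, 44 per group, ρ = 0.5.**

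- Group-by-time test on 3 df, constant difference after baseline: 36%.
- Baseline-adjusted mean of the three post-baseline visits, variance factor (1 + 2ρ)/3 − ρ² = 0.417: 71%.
- Single visit: 37%.

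**Step 4: readings that reach 90%.** Each changes the printed metric or design.

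- Cohen's f = 0.35, which is 0.70 SD for two groups: 98% time-averaged at ρ = 0.5.
- Single-visit t-test at 0.70 SD: 90.1%.
- Within-between interaction with f = 0.175: 90% at ρ = 0.25 and 98% at ρ = 0.5.

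**Step 5: raw units.** 2.3/5 = 0.46 and 6.9/15 = 0.46. An effect of 0.35 SD gives 0.35 × 5 = 1.75 to 0.35 × 15 = 5.25. An effect of 0.70 SD gives 3.5 to 10.5. The printed range fits neither.

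**Step 6: numbers of participants.** 140 × 0.72 = 101 and 101 × 0.88 = 89, so the attrition chain reproduces and 140 is the number to enrol. Keeping treatment dropouts and removing only follow-up loss gives 140 × 0.88 = 123. Then 123/88 = 1.40, which is 40% larger. The 28% appears only in the other direction: 1 − 88/123 = 0.28. All 140 is 140/88 = 1.59, or 59% larger.

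**The case against.** The strongest reply is that the plan names no test, so 54% belongs to a test chosen by the reader. A 2 × 4 treatment-by-time design and talk of longitudinal profiles suggest an interaction at least as readily as a group main effect. The time-averaged calculation also assumes the 0.35 SD gap at all four visits, including baseline, where randomisation makes the expected gap zero. If the gap exists only at the three later visits, the four-visit average is 0.35 × 3/4 = 0.26 SD and power at ρ = 0.5 is 34%. This stands: 54% is one scenario. But the tests that keep 0.35 SD as printed give about 34% to 71% at ρ = 0.5, so the choice of test does not restore 90%.

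The f = 0.175 interaction deserves weight, because f = d/2 is the usual two-group conversion and the reference list includes a G*Power paper. It shows that ρ = 0 is not the only possible source of the 90%. An interaction f of 0.175 is still not a constant 0.35 SD difference between groups, so it does not support the printed definition.

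The 0.46 SD figure may also have a legitimate origin. By normal approximation, a baseline-adjusted mean of the three later visits with 44 per group detects 0.457 SD at ρ = 0.25 and 0.446 SD at ρ = 0.5 with 90% power. If that was the calculation, 0.35 is still wrong, and the Data Analytic Plan rules out that adjustment.

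Finally, power is high for large effects. At 0.70 SD and ρ = 0.5 it is 98% time-averaged and 93% for the 3-df interaction with a constant difference after baseline. The 140/89 and 28% points are wording errors that do not change power, and understating the ITT surplus is conservative.

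**Conclusion.** The concern holds. On the printed definition, 44 per group does not give 90% power for 0.35 SD at the stated correlation bound. For the time-averaged comparison it gives about 54%, and the 90% detectable difference is about 0.55 SD. On that test the other printed effect, 0.46 SD, has 77% power at ρ = 0.5 and would need about 62 to 64 per group for 90%.

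The 54% depends on the time-averaged test, equal correlation of 0.5, complete data and a gap at every visit. How the plan obtained its 90% cannot be determined from the documents. Three points need no choice of test: 0.35 SD and 0.46 SD contradict each other, 140 completers contradicts 89, and the 28% note uses the wrong base. The shortfall matters for differences well below the 0.7 quoted from the pilot.

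**What to change.** First name the test and the effect metric behind the calculation, then print figures that agree.

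- **Time-averaged comparison in SD units:** state that with 44 per group, four time points, two-sided alpha 0.05 and correlation 0.5, power is about 54% for 0.35 SD and 90% for about 0.55 SD (2.8 to 8.3 raw units for SDs of 5 to 15).
- **If 0.35 was meant as Cohen's f:** correct the label and the parenthetical definition, and give 3.5 to 10.5 raw units.
- **If 2.3 to 6.9 was meant for the sample that keeps treatment dropouts:** say so and state about 62 per group.
- **If another test was used:** give its name, its assumed effect at each visit and its power.

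In Research Design and Methods, replace the statement that 140 will complete with 140 randomised and about 89 expected to complete all measures. Replace the 28% note with about 123 participants, roughly 40% more than 88 (all 140 would be 59% more).

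The Data Analytic Plan reports analyses already done, so label this a dated correction. The cost is a few sentences, and a less favourable power figure if 0.35 SD is kept. Enrolment and analysis are unchanged.
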